8.4.3 Other Endpoints

Cytokine and breast cancer biomarker (eg, MUC-1) levels will be explored in serum samples. For study sites participating in additional immunologic assessments, please refer to [Appendix 6](#). INXN-1001 PK analysis will be performed in Cycle 1 for all subjects enrolled the Safety Run-in (Part 1).

8.4.4 Safety Endpoints

The safety endpoints will include AEs, vital signs, ECG, physical examinations, laboratory data, and concomitant medications. All AEs will be coded according to Medical Dictionary

for Regulatory Activities (MedDRA®, version 13.0 or later). Concomitant medications will be coded using the World Health Organization Drug Dictionary, September 2006 or later.

The incidence, onset timing, duration, severity, relationship, and outcome will be listed for each AE. All treatment-emergent AEs (TEAEs) occurring on-study will be analyzed by treatment group and listed in by-subject data listings. Events that are considered related to treatment (possibly related or related) will also be tabulated.

Treatment-emergent AEs will be tabulated overall and by subject. ‘Treatment-emergent’ is defined as any AE that occurs during or after administration of the first dose of study drug through the Post-Treatment Safety Assessment visit (28 days after last dose of study drug); any event after the first dose of study drug that is considered study drug-related regardless of the start date of the event; or any event that is present at baseline that worsens in intensity or is subsequently considered to be drug related by the investigator. Serious TEAEs and related TEAEs will be summarized in a similar fashion. AEs to be presented will include TEAEs, treatment-emergent SAEs, and treatment-emergent related AEs, as well as the severity of the events. Timing relative to study treatment administration will also be presented. Treatment-related SAEs will also be summarized by treatment group and presented on a case-by-case basis in listings and narratives.

Dosing and study drug tolerability will also be assessed.

8.5 Procedures for Handling Missing, Unused, and Spurious Data

No imputation of values for missing data will be performed. Standard clinical monitoring and data management practices will be used to ensure the integrity of data.

8.6 Statistical Analyses

8.6.1 Subject Status

Subject status will be summarized for all randomized subjects by Study Arm. The numbers of subjects in the Efficacy population and Safety population will be summarized, as well as those receiving a non-randomized treatment.

In addition, major protocol violations will be summarized by Study Arm and presented in listings.

8.6.2 Baseline Characteristics

Demographic and baseline disease characteristic data will be summarized. Data to be tabulated will include at least demographic features such as sex, age, and race, as well as disease-specific status and medical history.

8.6.3 Safety Analyses

Safety tables will be presented for all safety parameters including TEAEs, dosing, vital signs, ECGs, and clinical laboratory tests. The Safety Population will be used for these analyses.

AEs will be coded using MedDRA® for the purpose of summarization. All AEs occurring during the study will be included in by-subject data listings. Treatment-emergent events will be tabulated. Deaths, SAEs, and AEs resulting in study discontinuation will be listed.

Safety variables will be tabulated and presented by study arm. Exposure to study drug and reasons for discontinuation of study treatment will be tabulated.

8.6.4 Efficacy Analyses

The Efficacy Evaluable Population will be used for the analyses of efficacy data by study arm.

8.6.4.1 Primary Efficacy Analyses

The primary analysis of the primary endpoint (16-week PFS rate) will be summarized using both a point estimate and its exact binomial 2-sided 95% confidence interval (CI). The 16-week PFS rate will be also estimated using the Kaplan-Meier method. The 95% CI of the PFS rate at 16 weeks will be calculated using the Greenwood formula.

8.6.4.2 Secondary and Other Analyses

PFS is defined per subject as the time (in months) from first dosing date to the date of progression. Subjects who died without a reported prior progression will be considered to have progressed on their date of death. Subjects who did not progress or die will be censored on the date of their last tumor assessment. Duration of response will be computed from the time measurement criteria were met for PR or CR until the date of documented PD or 1 year. Subjects who neither progressed nor died will be censored on the date of last tumor assessment.

INXN-1001 PK parameters to be determined will include, but are not limited to, the maximum concentration (C_{max}), time to maximum concentration (T_{max}), half-life ($t_{1/2}$), area-under-the-concentration time curve (AUC), volume of distribution (V_d), and clearance (CL). Where possible, descriptive statistics of the PK parameters will be provided; individual subject INXN-1001 concentrations, actual sampling times, and PK parameters will be listed.

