- 23. A Follow-Up Tumor Assessment visit will be performed 35 ± 7 days after the Post-Treatment Safety Assessment visit. This assessment is required for all subjects, including those with prior objective evidence of disease progression to ensure that more slowly declining tumor burden in response to therapy is not missed.

NOTE: Subjects without objective evidence of disease progression should continue to have tumor assessments performed at 8 to 10-week intervals until disease progression has been confirmed or an alternate anticancer therapy has been initiated, whichever occurs first.
- 24. Interim cancer history information will include documentation of any new concomitant medications and any anticancer treatments received since the Post-Treatment Safety Assessment visit or the previous tumor assessment.

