6.3 Concomitant Therapy

Concomitant medication information, including blood products, vitamins, and other supplements, will be collected for the time period beginning 28 days prior to the first dose of study drug through the Post-Treatment Safety Assessment visit.

Permitted:

- Subjects may receive standard treatments, including palliative and supportive care for any underlying illness, with the exception of palliative radiotherapy, which is NOT permitted.
- Antidiarrheal therapy is permitted for study drug-induced diarrhea.
- Antiemetics are permitted for study drug-induced nausea and vomiting. (except those listed [Appendix 2](#))
- Treatment with vitamin/mineral supplements is acceptable provided that they do not interfere with study endpoints, in the opinion of the investigator.

Not Permitted:

- Subjects may not receive medications, foods, or drinks that induce, inhibit, or are substrates of the CYP450 3A4 pathway within 7 days prior to the first dose of study drug through 96 hours after their last dose of INXN-1001. See [Appendix 2](#) for examples.
- Subjects may not receive any other investigational agent or anticancer therapy (chemotherapy, radiotherapy, etc.) while receiving study treatment.

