6.4.3 Efficacy Assessments

Appropriate cancer staging procedures should be performed during screening. For the purpose of this clinical trial, the following imaging is expected at screening:

- a. CT of the chest, and CT (or MRI) of the abdomen
- b. MRI (or CT) of the brain if brain metastasis are known or suspected

c. CT or MRI of other anatomical regions as clinically indicated

For each subject, disease sites are to be assessed throughout the study using the same method(s) of assessment used at screening. Chest and abdomen imaging are required for all follow-up imaging time points; images of the brain and other anatomical regions should be acquired on follow-up if positive at screening and as clinically indicated.

Target and non-target lesions should be selected and measured as per mRECIST v1.1 guidelines³⁹ (see [Appendix 4](#)). Lesions that will be/are injected with INXN-2001 and/or biopsied should not be selected as target lesions, but should be assessed as non-target lesions. For each subject, disease sites are to be assessed throughout the study using the same method(s) of assessment used at screening. Tumor response assessments will occur at 12 weeks, 16 weeks, and the Follow-up Tumor Assessment visit (24 weeks) for all subjects, including those who may have experienced a dose delay. Additional tumor response assessments may occur at the discretion of the investigator.

The investigator will evaluate each subject for response to therapy according to mRECIST v1.1 guidelines.

In the setting of this immunotherapy, a progression observed \leq week 12 requires confirmation at week 16 (see [Appendix 4](#) for further details). Subjects without objective evidence of disease progression at the Follow-Up Tumor Assessment visit should continue to have tumor assessments performed at 8-10 week intervals until disease progression has been documented, or an alternate anticancer therapy has been initiated, or up to 1 year, whichever occurs first.

In addition to radiological imaging techniques, photographs of visible cutaneous lesions should also be obtained. Digital photograph(s) with included measuring tape should be taken of all visible injected and non-injected tumors, and of any remaining visible local reactions in or around the injected lesion(s). Important guidelines regarding photographic methodology will be provided in a separate manual.

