8.4 Study Endpoints

8.4.1 Primary Efficacy Endpoint

The primary efficacy endpoint is the 16-week PFS rate, calculated as the number of subjects who had not progressed or died prior to 16 weeks from the date of their first dose, divided by the number of subjects in the study arm. Subjects who neither progressed nor died, but had their last tumor assessment prior to 16 weeks, will not be categorized as progression-free and will not be included in the numerator. Progressive disease (PD) will be determined by mRECIST v1.1 (please refer to [Appendix 4](#)).

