8.4.2 Secondary Efficacy Endpoints

Tumor-related secondary efficacy endpoints are defined as the following:

- PFS: time from the date of first dose to the date of PD or death (if prior to progression). Subjects without PD or death occurring as of the time of analysis will be censored as of the last date of disease evaluation. PD will be evaluated by mRECIST v1.1
- ORR by mRECIST v1.1: Proportion of subjects achieving a confirmed PR or CR according to mRECIST v1.1 during study. All objective responses (CR or PR) require confirmation by a repeat tumor assessment at least 4 weeks (28 days) after the response is first observed in order for the response to be considered confirmed.
- Duration of response: time from the date of first objective response (PR or CR) by mRECIST v1.1, until the date of PD or 1 year. Duration of response in subjects who have not progressed or died at the time of analysis will be censored as of the date of their last tumor assessment.
- Clinical benefit rate (CBR = proportion of subjects with CR, PR or SD) by mRECIST v1.1

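### The 16-week PFS rate has no rule for other anticancer therapy started before the week-16 assessment, so week-12 progression that resolves on another drug is scored progression-free

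*Protocol*

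**What the plan says.** **Primary rate.** Protocol Section 8.4.1 defines it as "calculated as the number of subjects who had not progressed or died prior to 16 weeks from the date of their first dose", with the arm's subject count as denominator. It adds one safeguard: "Subjects who neither progressed nor died, but had their last tumor assessment prior to 16 weeks, will not be categorized as progression-free". New anticancer therapy is not mentioned.

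**PFS and the Kaplan-Meier rate.** Section 8.4.2 says "Subjects without PD or death occurring as of the time of analysis will be censored as of the last date of disease evaluation", and Section 8.6.4.2 says "Subjects who did not progress or die will be censored on the date of their last tumor assessment". Section 8.6.4.1 adds: "The 16-week PFS rate will be also estimated using the Kaplan-Meier method". That estimate needs a censoring rule, and the only ones stated take no account of therapy.

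**Scans.** Section 6.4.3 says "Tumor response assessments will occur at 12 weeks, 16 weeks, and the Follow-up Tumor Assessment visit (24 weeks) for all subjects". Footnote 23 to Tables 2A and 2B says of the follow-up visit: "This assessment is required for all subjects, including those with prior objective evidence of disease progression".

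**Confirmation.** Footnote 15, Section 6.4.3 and the response table in Appendix 4 all require progression seen at week 12 to be confirmed at week 16.

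**Other therapy.** Section 6.3 says "Subjects may not receive any other investigational agent or anticancer therapy (chemotherapy, radiotherapy, etc.) while receiving study treatment". The bar lapses once study treatment stops. Section 9.4 ends follow-up at alternate therapy, but only for subjects who leave or finish study treatment without documented progression. Footnote 24 asks for interim anticancer treatments to be documented at the follow-up visit. No analysis section uses that record.

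**The concern.** The primary rate is meant to show what the study regimen achieves by week 16. If a scan taken on a different drug can supply the missing evidence of non-progression, the count credits the regimen with another drug's effect.

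Each arm is analysed separately against a fixed rate of no interest, 15% in Arm A and 40% in Arm C, with no untreated or standard-therapy control to absorb such credit. The final cut-offs are small counts (9 of 33 and 15 of 26), so a few misclassified subjects can move the decision. In an open-label trial, a scoring choice left until results are visible is also open to question.

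**Working it through.** **1. Week-12 progression followed by a switch.**
- Progression is seen at week 12 (C5D1). Under Appendix 4 it does not count unless confirmed at week 16.
- Section 5.3 allows withdrawal from study treatment for clinically significant progression. Section 6.3 then no longer bars other therapy.
- The week-16 scan is still due, because Section 6.4.3 schedules it for all subjects. Section 9.4's stop does not apply to a subject with objective progression.
- If that scan does not show progression, the week-12 finding is unconfirmed. The subject has not died and has a week-16 assessment.
- Section 8.4.1 then puts the subject in the numerator.

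If the same subject has no week-16 scan, Section 8.4.1 leaves them out of the numerator. The Kaplan-Meier treatment of the unconfirmed progression is not stated.

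**2. No progression, stops early and switches.**
- If Section 9.4 is followed, scanning ends at the switch. With no assessment at or after week 16, Section 8.4.1 makes the subject a failure.
- If the all-subject schedule (footnotes 15 and 23, Section 6.4.3) is followed, a later scan without progression makes the subject a success.
- The score depends on which text the site follows.

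Timing from footnotes 22 and 23: the follow-up visit falls 28 + 35 = 63 days after the last dose. Taking the last INXN-1001 dose on Day 7 of the final cycle:

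| Last cycle | Last dose (study day) | Follow-up visit |
|---|---|---|
| 1 | 7 | day 70, week 10 |
| 2 | 28 | day 91, week 13 |
| 3 | 49 | day 112, week 16 |

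So on that timing the follow-up visit reaches week 16 only if treatment stops after about Cycle 3 or later, although Section 6.4.3 labels the visit week 24.

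**3. The plan's own operating characteristics.** Inputs are the stage sizes and rates in Section 8.1 and the final cut-offs in the synopsis. Let X1 be successes among the n1 Stage 1 subjects, X2 successes among the n − n1 Stage 2 subjects, c1 the Stage 1 cut-off and c the final cut-off. Then

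P(go | p) = Σ over x ≥ c1 of P(X1 = x) × P(X2 ≥ c − x), with both counts binomial at rate p.

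- Arm A (≥3 of 13, then ≥9 of 33): 4.1% at p = 0.15 and 80.8% at p = 0.35.
- Arm C (≥6 of 12, then ≥15 of 26): 4.7% at p = 0.40 and 80.9% at p = 0.65.

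Both agree with the stated 80% power at one-sided 5%, reading 5% as a ceiling.

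**4. Sensitivity of the false-go probability.** Suppose a share f of true failures is scored as success. The apparent null rate is p0 + f(1 − p0). The documents give no value for f.

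| f | Arm A apparent rate | Arm A false-go | Arm C apparent rate | Arm C false-go |
|---|---|---|---|---|
| 0 | 0.1500 | 4.1% | 0.400 | 4.7% |
| 1% | 0.1585 | 5.6% | 0.406 | 5.3% |
| 2% | 0.1670 | 7.3% | 0.412 | 6.1% |
| 5% | 0.1925 | 14.4% | 0.430 | 8.6% |
| 10% | 0.2350 | 31.9% | 0.460 | 14.5% |

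In subjects, f = 5% means 33 × 0.85 × 0.05 = 1.4 in Arm A and 26 × 0.60 × 0.05 = 0.8 in Arm C. If the synopsis's extra Arm A look (≥1 of the first 6) is included, Arm A is 3.9% at zero, 13.6% at 5% and 30.3% at 10%.

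**The case against.** **The protocol is silent; it does not direct that such scans count.** A reader might infer that the rules expressly credit scans after new therapy. They do not, and for non-progressors Section 9.4 combined with Section 8.4.1 points to failure. This stands. It leaves the week-12 progression case open, because Section 9.4 does not cover it, and it leaves a conflict in the other case.

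**The open route is narrow.** Section 4.1.2 lets subjects with progression complete all six cycles unless the progression is clinically significant, so much week-12 progression would be re-scanned at week 16 still on study drug. The route needs a stop, a new drug, a week-16 scan, and enough change in about four weeks to undo the finding. This stands, and it argues for the low end of the table.

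**The early stopper is not a sure success.** A reader might infer that anyone who stops, switches and has a clear follow-up scan is counted. Section 9.4 can be read against that, and a follow-up visit after a stop in Cycle 1 or 2 would fall before week 16.

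**The censoring sentence in Section 8.6.4.2 does not define the primary rate.** It governs secondary PFS and, by implication, the Kaplan-Meier estimate. The primary point rests on Section 8.4.1.

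**A fuller plan may exist.** Section 8.8 defers to a formal statistical plan. The SAP supplied cannot fill the gap, since it describes a single-arm, single-center Phase Ib/II study with 12-week endpoints. Its Section 5.2 does treat chemotherapy resumed before week 12 after unequivocal progression as failure; this protocol has no counterpart.

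**Conclusion.** The concern holds in a limited form. Followed literally, Section 8.4.1 and the confirmation rule score as progression-free a subject whose week-12 progression is no longer seen at week 16 after a switch to another drug. For a non-progressor who switches, the protocol gives two answers.

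The size is unknown. The table shows sensitivity and does not estimate this trial's error rate. A reader might take 14.4% or 31.9% as Arm A's actual false-go risk, but the documents give no share of failures to support either figure. At 1% to 2% the false-go probability is 5.6% to 7.3% in Arm A and 5.3% to 6.1% in Arm C. The calculation assumes independent subjects, applies f to all true failures, and omits the six-subject look unless stated. Nor does meeting the cut-off trigger a trial automatically: the synopsis says only that a confirmatory trial would be considered.

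The rule should be settled before results are seen, because the direction is towards a false go and the cut-offs are small counts.

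**What to change.** 1. In Section 8.4.1, count a subject who starts other anticancer therapy before the week-16 assessment as not progression-free.
2. In Sections 8.4.2, 8.6.4.1 and 8.6.4.2, use only assessments made before new therapy for PFS and the Kaplan-Meier 16-week rate. Treat progression followed by new therapy without a confirmatory scan as an event at the date progression was first seen. Report the alternative handling as a sensitivity analysis.
3. Record the start date of any new anticancer therapy. Footnote 24 documents the treatments received but names no start date, so a reader should not assume that the variable already exists.
4. Reconcile footnotes 15 and 23 and Section 6.4.3 with Section 9.4 on whether scans continue after alternate therapy begins.

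**Cost.** A few sentences, one date field and one derived variable. The observed rate and power fall if subjects who would otherwise have been true successes start other therapy before week 16. If 5% of successes are lost this way, the target rate becomes 0.35 × 0.95 = 0.3325 in Arm A and 0.65 × 0.95 = 0.6175 in Arm C, and power becomes 75.4% and 70.4%. That 5% is also an assumption.

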8.7 Immunologic Responses

The trial will assess the cytokine profiles and breast cancer-associated biomarkers (eg, MUC-1) for all subjects.

In addition, participating sites will include additional immunologic assessments as described in [Appendix 6](#). The immunological effects of each treatment cycle on the cellular and humoral immune responses in the peripheral circulation and in tumor biopsy specimens.

Cytokine profiling will be performed by ELISA. Whole blood will be collected for flow cytometry analysis, immune response assay, and/or ELISPOT assays for measurement of the response to breast cancer-associated antigens. Samples will also be screened for the relative percentages of mononuclear immune cell subpopulations. At each time point, the change in immunologic response (CTL and Treg frequency in blood) from baseline and from the preceding time point will be correlated with the INXN-1001 dosage level, as well as with serum cytokine levels. In addition, tumor PBx or FNAs will be examined for cytokine expression, presence of injected adenovirus and CTL frequency, Treg and myeloid-derived suppressor cell frequency, and other immunological markers. The change in each measure from baseline and from the preceding biopsy will be correlated with the treatment arm.

8.8 Procedures for Reporting Deviations to Original Statistical Analysis Plan

A formal statistical plan for the analysis and presentation of data from this study will be prepared prior to database lock. Deviations from the statistical analyses outlined in this protocol will be indicated in this plan; any further modifications will be noted in the final clinical study report.

9. STUDY ADMINISTRATION

9.1 Electronic Case Report Forms and Source Documentation

For each subject, eCRFs and corresponding source records will be maintained at each clinical site. The Sponsor or designee will provide the study sites with secure access to and sufficient training on the electronic data capture (EDC) application, to permit site personnel to enter or correct information in the eCRFs for the subjects for whom they are responsible.

eCRFs should be completed in a timely manner, and every effort should be made to have forms completed and up-to-date in anticipation of a visit by the Sponsor's monitor. Specific instructions will be provided to the site. All requested information must be entered on the eCRF in the spaces provided. If an item is not available or is not applicable, it should be documented as such; do not leave a space blank.

It is the investigator's responsibility to ensure the accuracy, completeness, clarity, and timeliness of the data reported in the subject's eCRF. Through the EDC application, the investigator must provide formal approval of all subject information in the eCRFs and changes to the eCRFs to endorse the final submitted data for the subjects for whom he/she is responsible. The audit trail entry will show the user's identification information and the date and time of any corrections.

eCRF completion may be delegated to other study personnel; however, such delegation must be documented in writing. If, for any reason, certain data are lacking to complete an individual report form, the investigator will provide a written statement explaining the reasons for the lack of data.

Sponsor or designee will retain the eCRF data and corresponding audit trails. A copy of the final archival eCRF in the form of a compact disk or other electronic media will be placed in the investigator's study file.

